**Secondary Endpoint(s):**

We hypothesize that volunteers in both treatment conditions will demonstrate positive global counseling behaviors: demographics, The Empathy scale; however, those trained in BE WITH will more often employ suicide intervention practices when needed: SIRI-2.

### 2. 9.2 SAMPLE SIZE DETERMINATION

To determine appropriate sample sizes, we used formulas developed for PN-RCTs with continuous outcomes and binary outcomes as well as results from a closely related study that tested the effect of the ASIST intervention with similar outcome measures. To detect an effect size of .40 with a continuous outcome, utilizing a Type I error rate of .05, power of .80, ICC of .20, and R^2 of .50 (for baseline covariate), we need 270 older adults with 30 volunteers each calling 6 older adults. For a binary outcome under the same assumptions, we would require 414-522 older adults with 46-58 volunteers for most estimates of the probability of an outcome in the treatment and control groups. Recruiting 540 older

adults (180 in each condition) and 60 volunteers (30 for each treatment condition) provides an adequate sample to evaluate major effects of interest in all proposed analyses.

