## 1 PROTOCOL SUMMARY

### 1.1 SYNOPSIS

Title:	ADDRESSING SOCIAL ISOLATION, LONELINESS, AND ELEVATED SUICIDE RISK AMONG VULNERABLE OLDER ADULTS THROUGH AN 8 WEEK CARING CONTACTS TREATMENT: A PARTIALLY NESTED RANDOMIZED CONTROLLED TRIAL
Grant Number:	90INNU0021-03-00
Study Description:	
This PN-RCT evaluates an 8-week caring contacts treatment that is delivered to older adults (urban racially diverse, suburban, and/or rural) in 20-30 minute warm calling "dosages", over 3 conditions. Conditions include 2 treatment (i.e. treatment provided by helpers trained in a standardized and manualized Belongingness and Empathy training grounded in narrative reminiscence and the befriending literature (BE), and treatment provided by helpers trained in BE plus a standardized, manualized, and evidence-based suicide intervention training, the Aging Variant of LivingWorks ASIST (BE WITH), and 1 control (no treatment). Hypotheses include: (a) participants in the BE and BE WITH treatment conditions will experience significantly more improvement across measures than those in the control condition over the course of the 8-week treatment and (b) outcome improvements for those in treatment conditions will be more pronounced for those who begin the period at greater risk.

Objectives * :	
Primary Objective: To develop BE WITH Innovation and equip the Aging Services Network (ASN) with proven skills to reduce social isolation, loneliness, and elevated suicidality and promote social support/well-being with older adults receiving nutrition services.
 
Secondary Objectives: To validate and replicate BE WITH

Endpoints * :	
Primary Endpoint: Reduction in social isolation, loneliness, and elevated suicidality and improved social support/well-being for older adult participants receiving nutrition services.
 
Secondary Endpoints: Improved frequency of empathic and suicide intervention best practice behaviors by trained volunteers

Study Population:	Target $n = 540$ to adequately power the PN-RCT; men and women, aged 65 or older, receiving nutrition services, without instance of dementia or cognitive impairment, and in the state in the Southeastern US.
Description of Sites/Facilities Enrolling Participants:	There will be three Area Agencies on Aging, and 25 senior centers that will be involved in this clinical trial.

**Description of Study  
Intervention/Experimental  

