Since the clinical trial is structured to occur in cohorts, the longitudinal multilevel modeling (growth modeling) analysis will be run after each cohort is completed. Despite early cohorts being underpowered, we find significant value in understanding if the data are trending in the expected directions, and/or if there are any issues that need to be addressed. The methodologist running the analysis will remain unblinded throughout the analysis process. There are no temporary suspension or safety findings that would prompt temporary suspension of the treatment. The frequency of monitoring the end points is daily as older adult participants are on a rolling recruitment and finishing their treatment at different points in time. There is no effect of the interim analysis on the final analysis as it is the same analysis. Type I error results when running many different types of tests, however we are running the main analysis with an underpowered sample so that we are learning and understanding as we go. The final analysis will be the same code just with all the participants across all 4 cohorts.

---

7. 9.4.7 SUB-GROUP ANALYSES

Sub-group analyses on the primary endpoints will be assessed in two ways: (a) multi-level modeling by treatment severity group (same primary analysis, conducted independently for low, medium, and high risk patients), and (b) cluster analysis to explore any potential differential treatment effects across predefined patient subgroups (e.g., age, sex, race, etc.). Interaction terms between any subgroup variables (i.e. age, sex, baseline severity) and treatment condition will be included to assess whether the trajectory of outcomes over time varied by subgroup. This approach will enable the examination of both between- and within-patient variability while accounting for repeated measures and clustering.

Since the secondary endpoints are serving as a fidelity check (i.e. trained helpers increased skills, retained skills, etc.) and were are only planning for approximately 60 trained helpers, which would be under powered, any differences in sub-groups, we imagine will be challenging to detect. Despite this,

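### Section 9.2 sizes only the called-versus-control effect on older adults; its adequacy claim for all analyses is not supported for the risk hypothesis or the helper contrast

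*Combined protocol and SAP*

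**What the plan says.** Section 9.2 bases its calculation for older adults on a standardised difference of 0.40 in a scale score. The error rates and clustering are set by "utilizing a Type I error rate of .05, power of .80, ICC of .20". The baseline measure is taken to explain half of the outcome variance (R² .50). The result is "we need 270 older adults with 30 volunteers each calling 6 older adults". The binary calculation gives 414-522 older adults and 46-58 volunteers. The section then settles on 540 older adults (180 per arm) and 60 volunteers (30 per called arm) and concludes that this "provides an adequate sample to evaluate major effects of interest in all proposed analyses".

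The synopsis has two hypotheses. The second is that "outcome improvements for those in treatment conditions will be more pronounced for those who begin the period at greater risk", and the objectives table in section 3 gives risk tier its own row. Section 9.4.7 plans the "same primary analysis, conducted independently for low, medium, and high risk patients", together with interaction terms between treatment and subgroup variables, among them baseline severity.

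The secondary endpoint (sections 1.1, 9.1 and 9.4.3) concerns helper skill: BE WITH helpers are expected to use suicide intervention practices more than BE helpers. Section 9.4.7 says of helper subgroups that there are "approximately 60 trained helpers, which would be under powered".

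Section 9.4.1 sets the significance threshold at .01, whereas section 9.2 plans at .05.

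**The concern.** A sample sized for a difference between two arms is not thereby sized for a difference between tiers in that difference, which has a much larger variance. Nor is it sized for a comparison whose units are 30 helpers against 30. Section 9.2 nevertheless covers both with one sentence. If either analysis came out non-significant, a reader who relied on that sentence could take the result as evidence of no difference from an adequate sample. The risk hypothesis is one of only two in the synopsis, and the helper comparison is the stated secondary endpoint, so neither is peripheral.

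**Working it through.** **Inputs from section 9.2.** d = 0.40, alpha .05 (two-sided assumed), power .80, ICC .20, R² .50, 6 older adults per caller, 180 per arm, 30 callers per called arm. From section 9.4.1: testing threshold .01. Assumptions: R² applies at both levels, 540 are analysed, tiers are of equal size and mixed within caseloads.

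**The plan's own figure.** With J callers per called arm, one called arm versus control has variance

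(1 − R²)[1 + (6 − 1)·ICC]/(6J) + (1 − R²)/(6J) = (0.50 × 2 + 0.50)/(6J) = 1.5/(6J).

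Using a t reference with J − 1 degrees of freedom, power is .790 at J = 14 and .821 at J = 15. So J = 15, which is 90 per arm, 270 older adults and 30 callers: the stated figure is reproduced exactly. At J = 30 the SE is √(1.5/180) = 0.091, and power for 0.40 is .99 at .05 and .94 at .01. The binary figure cannot be checked because its event probabilities are not given.

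**Risk hypothesis.** The caller component (0.20 × 0.50 = 0.10) cancels when tiers are compared within caseloads. The variance per person is then 0.80 × 0.50 = 0.40 if called and 0.50 in control. The SE of the tier difference in treatment effect is the square root of the summed cell variances. Examples:

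- Two equal tiers, one arm: √[2(0.40 + 0.50)/90] = 0.141.
- Two equal tiers, called arms pooled: √[2(0.40/180 + 0.50/90)] = 0.125.
- High versus low thirds, one arm: √[2(0.40 + 0.50)/60] = 0.173.

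The difference detectable with 80% power is 2.80 × SE at .05 and 3.42 × SE at .01. Each cell below gives .05 / .01.

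| Comparison | SE | Detectable (SD) | Power for 0.40 | Power for 0.20 |
|---|---|---|---|---|
| Two tiers, arms pooled | 0.125 | 0.349 / 0.426 | .894 / .736 | .361 / .165 |
| Medium+high v low, pooled | 0.132 | 0.371 / 0.452 | .856 / .673 | .327 / .144 |
| High v low thirds, pooled | 0.153 | 0.428 / 0.522 | .745 / .517 | .258 / .103 |
| Two tiers, one arm | 0.141 | 0.396 / 0.483 | .807 / .600 | .293 / .123 |
| Medium+high v low, one arm | 0.150 | 0.420 / 0.513 | .760 / .536 | .265 / .107 |
| High v low thirds, one arm | 0.173 | 0.485 / 0.592 | .637 / .395 | .210 / .078 |

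The documents give no interaction size. The 0.40 column takes it to be as large as the whole planned effect, and the 0.20 column takes half of that. Both are assumptions.

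**Helper contrast, 30 versus 30.** SE = √[(1 − R²) × 2/30], which is 0.258 with no covariate and 0.183 with R² .50. From the noncentral t with 58 degrees of freedom:

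| | Power at d = 0.40 (.05 / .01) | Detectable at 80% (.05 / .01) |
|---|---|---|
| Unadjusted | .33 / .14 | 0.74 / 0.91 |
| Baseline R² .50 | .58 / .33 | 0.52 / 0.64 |

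Both the 0.40 and the R² .50 were set for older-adult outcomes, so using them for helpers is an assumption.

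**The case against.** The strongest defence is that the sentence in 9.2 speaks of major effects of interest. Section 9.1 does not list the risk hypothesis, section 9.4.7 places it among the subgroup analyses, and the same section calls the secondary endpoints a fidelity check. That narrows the claim but does not support it. The risk hypothesis is half of the synopsis's hypotheses and has a row in section 3, the helper comparison is the named secondary endpoint, and 9.2 shows no power for either.

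Three stronger readings are tempting and do not hold.

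- A reader might infer that the risk hypothesis is badly underpowered on the plan's own values. The plan gives no interaction size. At .05, an interaction of 0.40 between two equal tiers has power .81 for one arm and .89 with the arms pooled. The very low figures need a smaller interaction, which is this review's assumption.
- A reader might take the remark in 9.4.7 about 60 helpers as conceding the main helper comparison. It concerns differences among helper subgroups only.
- A reader might conclude that helpers cannot be compared usefully. Section 4.3 reports a high effect size for earlier helper training, and a true difference of 0.74 SD (0.52 adjusted) would be detected with 80% power at .05. But that earlier result is pre-post, carries no number and is not BE WITH against BE, so it does not establish adequacy.

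Two further points stand. Section 9.4.1 already promises confidence intervals and effect sizes, so a null result would not be wholly uninformative. Also, the synopsis and section 3 could be read literally as comparing tiers among called participants only. With called arms pooled and medium+high against low, the SE is √(0.40/240 + 0.40/120) = 0.071, and power is about .81 even at 0.20 (alpha .05). That comparison does not use the randomised control, so it would not show that treatment works better at higher risk.

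**Conclusion.** The claim of adequacy is too broad; the sample size calculation itself is not in error, since 270 reproduces and 540 gives the called-versus-control effect ample power. What is unsupported is the extension to the risk hypothesis and the helper contrast.

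For helpers, power falls short of .80 at d = 0.40 under every setting examined. For the risk hypothesis the answer depends on a size that the plan does not state. If the interaction equals the whole 0.40 effect, power ranges from .64 to .89 at .05, but only from about .40 to .74 at the plan's own .01 threshold. If it is half that, power is .21 to .36 at .05 and .08 to .17 at .01.

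The tier figures rest on equal tiers, and the tiers themselves are unsettled. Section 8.1 makes low-risk people ineligible, while sections 3 and 9.4.7 compare and analyse a low tier.

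**What to change.** In section 9.2, limit the adequacy sentence to each called arm versus control on older-adult outcomes. Then add, with the assumptions listed:

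- the detectable tier difference in treatment effect: about 0.35 to 0.49 SD at .05 and 0.43 to 0.59 SD at .01. The lower ends are for two tiers with called arms pooled, the upper ends for one arm with high versus low thirds;
- the detectable helper difference: 0.74 SD unadjusted or 0.52 SD adjusted at .05 (0.91 or 0.64 at .01);
- a statement that null results for the risk hypothesis or the helper contrast will be interpreted from their confidence intervals and not as evidence of no difference.

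In section 9.4.7, base the risk hypothesis on a single full-sample interaction of treatment with a named continuous baseline score, and keep the tier-by-tier fits as descriptive. With a normal baseline and linear moderation this carries about 26% more information than comparing outer thirds and 57% more than comparing halves. If low-risk people are excluded, the baseline is truncated and the gain will differ.

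Reconcile section 8.1 with sections 3 and 9.4.7 on the low-risk tier, and use one alpha in 9.2 and 9.4.1 when quoting these figures.

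The cost is wording only, with no change to recruitment or data collection. The stated adequacy becomes less favourable, and the continuous interaction assumes roughly linear moderation.

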### 3. 9.3 POPULATIONS FOR ANALYSES

The population for analysis includes all randomized participants who met inclusion criteria. We are using the Intention-to-Treat (ITT) Approach, meaning that even those participants that had an AE or dropped out of the treatment will still be included.

### 4. 9.4 STATISTICAL ANALYSES

#### 1. 9.4.1 GENERAL APPROACH

For descriptive statistics, categorical and continuous data will be presented percentages, means with standard deviations, and ranges. For qualitative research, procedural and interpretive rigor will be monitored and maintained with the use of particular CQR methodology such as Consensual Qualitative Research paired with odds ratio analysis to ensure that there are no demographic or treatment confounders. For inferential tests, we will use p-value at .01 and confidence intervals for statistical significance, along with effect sizes, etc. Covariates and confounders are pre-specified in the sections below. Checks of assumptions (e.g., normality) underlying statistical procedures will be performed and any corrective procedures needed and recommended by our biostatistician will be applied.

#### 2. 9.4.2 ANALYSIS OF THE PRIMARY ENDPOINT(S)

This validation study is a partially nested randomized controlled trial design (PN-RCT) with a two-level structure of clients (level-1) nested within callers (level-2) for the two treatment conditions which receive calls. Given that outcomes for older adults receiving calls from the same volunteer may be more similar than for those who receive calls from a different volunteer, the use of multilevel modeling can account for these data dependencies. Analyses will investigate the effect of treatment conditions (BE, BE WITH, and control) on post-intervention outcomes while controlling for baseline responses (prior to intervention). Furthermore, analyses will explore differences between treatment conditions in longitudinal trends of client state as well as how volunteers utilize specific intervention skills over time. For this longitudinal data, a lower level of nesting will be included in the analysis: weekly call and state data (level 1) nested within older adults (level 2) nested within volunteers (level 3). However, the PN-RCT design would only have levels 1 and 2 for the control group.

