## 2. 6.3 MEASURES TO MINIMIZE BIAS: RANDOMIZATION AND BLINDING

We will use weighted stratified random assignment. After participants are baselined, we will score their data and assign them a risk tier (low, medium, high). Subsequently, we will randomize them to one of 3 conditions: BE condition, BE + ASIST condition, or control. Since the trial is being conducted in cohorts (waves), and to ensure the least amount of time between being baselined and starting the treatment, participants will be randomized one by one after they are baselined. The weighted component enables there to be equal representation of both risk tier and number of participants across all 3 treatment conditions within the confines of the ongoing nature of the trial.

At the time of baseline, participants are assigned 2 codes: one that is fully numeric, and another that is alphanumeric. The PI and graduate student(s) will have access to the unblinded data (i.e. both the older adults' names, codes, and baseline data) as the PI is supervising the process and a few graduate students will be helping with scoring, and the weighted stratified random assignment. The methodologist will only have access to the participants' codes and raw data. They will remain blind to ensure the most objective analysis of the data.

If a participant remains at elevated risk for suicide at the conclusion of the treatment, we will unblind them and report to their assigned case manager.

We will also use separate documents with participant codes only to track the following: treatment condition, rebaselines, any survey/measurement issues, risk tiers, etc. to ensure an additional level of rigor in protecting against any bias. Further, in all tracking files that the PI's research lab utilizes, only participant IDs will be utilized (i.e. tracking which participants are up for the next measurement occasion, etc.).

The only potential inadvertent unblinding that we could foresee would be with respect to the use of the Friendlybuzz system. The treatment providers do need to know the first names of the older adult participants, therefore ONLY their first names will be available. The data team, however, is completely distinct from the treatment team, and will not have access to the Friendlybuzz system.

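### Allocation is stratified by risk tier, but section 9.4.2 does not put tier in the primary model; adding it is a small, nearly free improvement

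*Combined protocol and SAP*

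**What the plan says.** **Allocation.** Section 6.3 scores each participant's baseline data, assigns a risk tier, and then randomises one person at a time with weights: "The weighted component enables there to be equal representation of both risk tier and number of participants across all 3 treatment conditions". The outcome table in section 4.1 also describes stratification by three levels of risk. Section 8.1 says the tier is scored from the UCLA, INQ and SPS.

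**Primary analysis.** Section 9.4.2 models post-intervention outcomes by condition "while controlling for baseline responses (prior to intervention". It names no other covariate. Section 9.4.1 promises that covariates and confounders are pre-specified further on.

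**Where tier does appear.** Section 3 has a growth-model hypothesis about tier. Section 9.4.7 plans separate models by tier and interactions of baseline severity with condition. None of these makes tier a main effect in the primary comparison.

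**Cohorts.** Section 9.4.6 says of the pooled analysis: "The final analysis will be the same code just with all the participants across all 4 cohorts". Section 6.3 mentions waves only to explain why participants are randomised one by one.

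**The concern.** Balancing the arms on a prognostic factor reduces the true sampling variability of the treatment contrast. If the model leaves that factor out, its between-tier variation stays in the residual, and the estimated standard error can exceed the true one. Tests then lean conservative and intervals are a little wide.

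Baseline adjustment may not remove all of this. The primary hypothesis in 9.1 also covers depression, anxiety and well-being. If baseline responses means only each outcome's own baseline value, a PHQ-9, GAD-7 or SF-12 model contains none of the three scales that determined the allocation stratum. Section 9.4.2 does not say which reading applies.

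At stake are a little precision and a covariate list settled in advance. The second matters somewhat more than usual because 9.4.6 runs the same model after every cohort.

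**Working it through.** **1. Reproduce the planned sample size.** Section 9.2 gives the inputs: "To detect an effect size of .40 with a continuous outcome"; "utilizing a Type I error rate of .05, power of .80, ICC of .20"; R² "of .50 (for baseline covariate"; result "we need 270 older adults with 30 volunteers each calling 6 older adults". A two-sided test is assumed. For one treated arm against control, with K callers per arm, m = 6 clients per caller and n_c = 6K controls:

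Var = (1 − R²) × [(1 + (m − 1) × ICC)/(K × m) + 1/n_c]

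With K = 15: 0.50 × [2.0/90 + 1/90] = 0.01667. A noncentral t with K − 1 = 14 df gives power 0.821. K = 14 gives 0.790. So K = 15 is the minimum and N = 18 × 15 = 270, which matches the plan.

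**2. Baseline adjustment alone at the planned size.** Section 9.2 plans "adults (180 in each condition) and 60 volunteers (30 for each treatment condition". With K = 30 and n_c = 180, Var = 0.50 × (2.0/180 + 1/180) = 0.00833 and SE = 0.0913 (29 df). Power is 0.988 at alpha .05 (the level in 9.2) and 0.939 at alpha .01 (the threshold in 9.4.1). With no covariate (R² = 0) it would be 0.850 and 0.635. The baseline covariate therefore supplies most of the available gain.

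**3. Add tier.** Let p be the share of residual variance that tier explains beyond baseline. The documents give no value, so p is an assumption. Two treatments of clustering bracket the effect:

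- *Proportional:* caller and client components shrink alike, so the SE is multiplied by √(1 − p).
- *Client level only:* the contrast variance is proportional to 1.2 (callers) + 0.8 (clients, treated) + 1.0 (control) = 3.0. Removing p from each of the two client terms leaves 3.0 − 2p, so the SE is multiplied by √(1 − 2p/3).

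| p | SE reduction, client only / proportional | Power at .05, client only / proportional | Power at .01, client only / proportional |
|---|---|---|---|
| 0 | 0 | 0.988 | 0.939 |
| 0.01 | 0.3% / 0.5% | 0.989 / 0.989 | 0.941 / 0.942 |
| 0.05 | 1.7% / 2.5% | 0.991 / 0.991 | 0.947 / 0.951 |
| 0.10 | 3.4% / 5.1% | 0.992 / 0.994 | 0.955 / 0.962 |

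**4. Is 1-5% plausible?** This was simulated under assumed correlations. When the other tier scales carry no information beyond the outcome's own baseline, tier adds nothing. When they carry 2% of outcome variance, tier adds about 1-3% of residual variance. At 5% it adds about 3-8%. With only two tiers enrolled, the added share stayed at or below about 7.5% in every case tried.

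**5. Type I error.** This simulation used 6,000 runs per row, allocation stratified by tier, and an individual-level model without caller clustering. Nominal level is 0.05 and simulation error about √(0.05 × 0.95/6000) = 0.003.

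| Share of outcome variance: other tier scales | Share: cohort | Baseline only | With tier and cohort |
|---|---|---|---|
| 0 | 0 | 0.051 | 0.052 |
| 0.05 | 0 | 0.049 | 0.054 |
| 0 | 0.025 | 0.050 | 0.051 |
| 0.05 | 0.025 | 0.045 | 0.052 |
| 0.10 | 0.05 | 0.042 | 0.051 |

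Leaving tier out is neutral to slightly conservative.

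**The case against.** The strongest reply is that tier is itself a coarse grouping of baseline scores. The outcomes named in section 3 (UCLA, INQ, SPS) are the scales it is built from, so for those outcomes the baseline covariate already does most of the work. Section 9.4.2 also uses a plural that could mean the whole baseline battery. This stands in large part and is why the gain is small. It does not settle the matter for PHQ-9, GAD-7 and SF-12, where the text leaves the covariate undefined.

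A reader might go further and infer three things that the documents do not support:

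- *The design's precision is thrown away.* Step 2 shows that baseline adjustment keeps most of it.
- *Cohort was also an allocation factor, so omitting it mismatches the randomisation.* Section 6.3 names only tier and arm size as balanced. Cohort adjustment may absorb calendar differences, but its benefit is unknown.
- *The primary test is invalid.* The simulated error rates show no inflation, and omitting a balanced covariate does not bias the comparison.

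A further fair objection is that tier and cohort are not single-valued for everyone. Section 6.2.1 allows re-baselining and re-randomisation to a new provider, and 7.2 allows re-enrolment in a later wave. The fix has to say which value counts.

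**Conclusion.** The point holds as a minor one, and acting on it is a free improvement. Tier is an allocation stratum, and 9.4.2 does not include it as a main effect. The consequence is at most slightly wide standard errors, chiefly for outcomes outside the tier scales.

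For p of 1-5%, the SE reduction is about 0.3-2.5%. The power gain at 540 is about one point or less: at most 0.951 − 0.939 = 0.012 at alpha .01 and 0.991 − 0.988 = 0.003 at alpha .05. Even at p = 10% the gain at alpha .01 is only about two points (0.962).

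These figures rest on the assumed p, a two-sided test, equal total variance in all arms, R² acting at both levels, and no allowance for dropout, for which the plan gives no rate. They apply to the post-intervention comparison.

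**What to change.** Add to 9.4.2: *Risk tier as used at the participant's first randomisation enters every primary model as a fixed effect, together with the baseline value of the outcome.* This wording says what the baseline adjustment contains, honours the promise in 9.4.1, and gives one tier value to anyone re-baselined or re-enrolled.

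Optionally, add cohort (wave of first randomisation) as a fixed effect for calendar differences, described as a choice and not as an allocation factor.

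Before finalising, reconcile section 8.1, which leaves low-risk people out of enrolment, with sections 3, 4.1, 6.3 and 9.4.7, which use three tiers. The answer decides how many tier levels enter the model.

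Cost: one or two degrees of freedom for tier, and three more if the four cohorts are added. Tier is already tracked under 6.3. No section explicitly lists cohort as a recorded variable, so it would need to be added to the analysis data set if used.
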